10.1 Extent of Exposure

Treatment exposure will be determined by duration of treatment and extent of exposure to study drug. Measures of extent of exposure includes the screening weight normalized average dose of study drug (mg) administered and the number of doses administered per subject.

The duration of exposure in weeks is defined as the (last dose date - first dose date + 1)/7.

eCRFs captures the volume of EQ001/Placebo prepared and volume administered at each dosing visit. As described in the Pharmacy Manual, volume prepared at a dosing visit is calculated based on the subject's weight (kg) and the randomized dose level (mg/kg); i.e., volume prepared (mL) = weight x dose level /100. The weight at screening is used to calculate the study drug dose, unless there has been a weight change of 20% or more from the screening weight, then the weight at visit is used.

The screening weight normalized average dose of study drug (mg/kg) administered at a dosing visit = total volume of study drug administered at all dosing visits (mL) x (100 mg/1 mL)/(the screening weight x number of doses administered).

Duration of exposure and screening weight normalized average dose of study drug administered per dose will be summarized by continuous summary statistics (n, mean, standard deviation (SD), median, minimum, and maximum). The number and percentage of doses administered will be summarized by treatment group for each cohort.

Cumulative volume administered will be summarized by continuous summary statistics by treatment group for each cohort.

10.2 Treatment Compliance

Overall treatment compliance will be calculated based on the cumulative volume of study drug administered (ml) and the cumulative volume of study drug prepared (ml).

Compliance (%) = 100 x (cumulative volume of drug administered / cumulative volume of drug prepared).

Treatment compliance will be summarized by continuous summary statistics (n, mean, standard deviation (SD), median, minimum, and maximum) by treatment group for each cohort.

A by-subject listing of exposure and compliance data will also be created.

10.3 Adverse Events

An adverse event is defined as any untoward medical occurrence in a subject. Dose limiting toxicity (DLT) is defined as any study drug related AE of CTCAE severity Grade of 3 or higher. The occurrence of Grade 3 lymphopenia is classified as a DLT only if present with concomitant infection at least possibly related to the underlying lymphopenia; Grade 4 or higher severity lymphopenia is classified as a DLT. Treatment-emergent AEs (TEAE) are defined as any AE that started after dosing or prior to dosing and that worsens following exposure to the study drug. If the start date of an AE is partially or completely missing, the date will be compared as far as possible with the date of the start of administration of study drug. The AE will be assumed to be treatment-emergent if it cannot be definitively shown that the AE did

not occur during the treatment-emergent period (worst case approach; see [Section 6.3](#) for imputation algorithm).

All AEs will be coded using MedDRA version 22.0 and graded using Common Terminology Criteria for Adverse Events (CTCAE) v5.0 severity grading scale, as annotated below:

- **Grade 1: Mild**; asymptomatic or mild symptoms; clinical or diagnostic observations only; intervention not indicated.
- **Grade 2: Moderate**; minimal, local, or noninvasive intervention indicated; limiting age-appropriate instrumental Activities of Daily Living (ADL). Instrumental ADL refers to preparing meals, shopping for groceries or clothes, using the telephone, managing money, etc.
- **Grade 3: Severe or medically significant**, but not immediately life-threatening; hospitalization or prolongation of hospitalization indicated; disabling; limiting self-care ADL. Self-care ADL refers to bathing, dressing and undressing, feeding oneself, using the toilet, taking medications, and not being bedridden.
- **Grade 4: Life-threatening consequences**; urgent intervention indicated.
- **Grade 5: Death** related to the AE.

For the purpose of the summaries AEs with missing relatedness will be considered to be related to study drug.

Analyses of AEs will include TEAEs summarized descriptively by number of subjects with an event (n), and percentage (%), by MedDRA SOC, PT and CTCAE grade.

A subject will be counted once at the SOC level and once at PT level. For summaries by SOC, PT, and CTCAE severity grade, a subject will be counted once at highest observed severity grade within an SOC and PT. Summaries by relatedness would be handled similar to the summaries by severity grade. Summaries by SOC and PT will be ordered by overall descending frequency of SOC and then, within a SOC, by overall descending frequency of PT.

Summaries of AEs will include:

- An overall summary providing subject incidence of the following:
 - Any TEAE
 - Any treatment-emergent serious AE (TESAE)
 - Any treatment-related TEAE
 - Any treatment-related TESAE
 - TEAE by maximum severity
 - Any TEAE leading to the end of treatment
 - Any TEAE leading to death
 - Any dose limiting toxicity (DLT)
 - [REDACTED]
- TEAEs by SOC and PT
- TEAEs Related to Study Drug
- TESAEs by SOC and PT

This document is confidential.

[REDACTED]

- TEAEs with Severity Grade ≥ 3 by SOC and PT
- TEAEs by SOC, PT and Worst Severity Grade
- TESAEs Related to Study Drug
- TEAEs Leading to End of Treatment by SOC and PT
- TEAEs Leading to Death by SOC and PT
- Dose Limiting Toxicities by SOC and PT

A by-subject listing of AE data will also be created. In general, adverse events occurring within 30 days after last dose of study drug will be included in the AE summaries but all AEs will be included in the listings. AEs occurring before start of study treatment will be included in the data listings but will not be included in the summary tables of AEs.

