The DRC will periodically review all available clinical and laboratory safety data during the study. When the last subject in a cohort completes the Day 29 assessments, the DRC will convene and make recommendations regarding cohort advancement and study continuation, discontinuation, or modification.

Dose-limiting toxicity is defined as any study drug-related adverse event (AE) of National Cancer Institute (NCI) Common Terminology Criteria for Adverse Events (CTCAE) Version 5.0 \geq Grade 3 severity (including \geq Grade 3 injection-related reaction or other clinical finding associated with hypersensitivity related to study drug) and not related to underlying asthma. The occurrence of Grade 3 lymphopenia will be classified as a DLT only if present with concomitant infection at least possibly related to the underlying lymphopenia; Grade 4 or higher severity of lymphopenia will be classified as a DLT. If 2 subjects experience DLTs in a single cohort (in the DLT assessment period; Study Days 1-29), the DRC will convene to review all available, unblinded safety, PK, PD, and clinical activity data. After its evaluation, the DRC may recommend study continuation (with or without modification) or termination of dose escalation. If dose escalation is terminated, the next-lower dose may be declared the MTD. Alternatively, an additional cohort at an intermediate dose may be added to better define the MTD.

Subject Stopping Criteria:

Dosing of EQ001 will be permanently discontinued in a subject if any of the following occurs:

- Any DLT (see definition above)
- Subject's consent withdrawn
- Investigator or Sponsor decides that the subject will not benefit from further investigational product (IP)
- Pregnancy
- Subject is unable to comply with the study requirements
- Sponsor terminates the study
- A regulatory authority mandates a study dosing cessation
- Subject experiences a DLT anytime during the treatment period

Number of Subjects Planned:

[figure not shown]
Up to 40 subjects with moderate-to-severe uncontrolled asthma are planned to be enrolled in the study.

Inclusion Criteria:

Subjects will be required to meet all of the following inclusion criteria in order to be eligible for study enrollment:

1. Is male or female, age \geq 18 and \leq 75 years

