9.7 Enrollment or Randomization and Blinding

It is the investigator's responsibility to ensure that subjects are eligible to participate in the study prior to enrollment and continue to remain eligible throughout the study. An IWRS will be used to ensure study drug inventory, accountability, and appropriate cohort allocation and blinded treatment assignment. The site's unblinded pharmacist or designee will have access to the IWRS and all treatment assignments.

The study will be randomized, double blinded, and placebo controlled. Subjects will be randomized in a 3:1 ratio (active:placebo).

After informed consent has been obtained, all Screening procedures have been assessed, and study eligibility has been confirmed, subjects will be randomized to receive either EQ001 or placebo on Study Day 1. The unblinded study pharmacist or designee will access the IWRS to randomize the subject into the study, receive the blinded treatment assignment and dose, record drug accountability, and request resupply.

Investigators, site staff, and subjects will be blinded to treatment assignment. The Sponsor will be unblinded to treatment assignment. The unblinded pharmacist or designee will be instructed not to divulge the treatment administered to any subject with the blinded site personnel, study subject or blinded study monitor and any other blinded CRO/vendor team members.

The blind should be broken only if knowledge of the subject's treatment allocation would facilitate specific emergency treatment. Unblinding procedures are provided in the Pharmacy Manual. The investigator must contact the Sponsor and/or designee prior to unblinding a subject's treatment assignment. In the event of an emergency when unblinding is necessary and the Sponsor and/or designee could not be contacted, the investigator should contact the Sponsor

and/or designee as soon as possible after the unblinding. Treatment assignment may be provided to the study sites/subjects after database lock.

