11.2 Causality Assessment

The investigator or qualified subinvestigator is responsible for assessing and assigning the causality relationship of the event to study drug using clinical judgment and the following categories of relatedness:

- Related: There is at least some possibility that the AE could be related to study drug administration.
- Not related: There is a high degree of certainty that the AE is NOT related to study drug administration.

The investigator or qualified subinvestigator is also responsible for assessing and assigning the causality relationship of the event to study-related procedures (eg, invasive procedures, such as venipuncture) using clinical judgment and the following categories of relatedness:

- Related: There is at least some possibility that the AE could be related to study drug administration.
- Not related: There is a high degree of certainty that the AE is NOT related to study drug administration.

In making a causality assessment of an AE, it should be considered as to whether or not the AE is expected to occur due to the underlying disease, based on the investigator's clinical experience in managing moderate-to-severe uncontrolled asthma (Section 10.5).

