11.5 Reporting Adverse Events

11.5.1 Reporting Procedures for Nonserious Adverse Events

The investigator is responsible for ensuring that all AEs observed by the investigator or designee or reported by the subject are reported using the AE eCRF.

The investigator will assign the following AE attributes:

- AE diagnosis or syndrome(s), if known (if not known, signs or symptoms)
- Dates of onset and resolution (if resolved)

Equillium AUS Pty Ltd	Clinical Study Protocol No. EQ001-19-001	Page 56 of 79
-----------------------	--	---------------

- Severity
- Causality relationship to study drug or study-related procedures
- Action taken
- Outcome

Follow-up of nonserious AEs will continue through the last day on the study and/or until a definitive outcome (eg, resolved, resolved with sequelae, lost to follow-up) is achieved.

When a subject is withdrawn from the study because of a nonserious AE, the Sponsor and/or designee must be notified by email or phone within 48 hours.

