2.2 Timing of Analyses and Data Review

When the last subject in each cohort completes the [REDACTED], all available safety, [REDACTED], [REDACTED] and clinical activity data from all cohorts will be compiled. Randomization in the next dose cohort will not begin until the Data Review Committee (DRC) review of all available safety data from all subjects support escalation to the next dose level. An independent unblinded team from [REDACTED] will perform the unblinded analyses as described in [Section 3.5](#) of this SAP (please refer to blinding section) to maintain the blinding of the study.

All the analyses presented in this SAP, will be performed after the database lock when all the data will be considered as unblinded. Analyses for the purpose of the DRC data reviews will be based on a data snapshot at the time of the data review.

3 Study Summary

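### The DLT definition in SAP 10.3 omits the protocol synopsis's exclusion of asthma-related events: a minor mismatch that changes the final DLT counts only if the tables are derived from the SAP wording

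*SAP*

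**What the plan says.** The protocol synopsis, under the DRC, DLT and stopping criteria, makes a DLT an adverse event that is related to study drug, is CTCAE v5.0 Grade 3 or higher, and is "and not related to underlying asthma". Grade 3 lymphopenia counts only with an associated infection; Grade 4 or higher always counts.

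SAP 10.3 states: "Dose limiting toxicity (DLT) is defined as any study drug related AE of CTCAE severity Grade of 3 or higher". It then repeats the lymphopenia rule. It has no asthma condition, and none appears elsewhere in the visible SAP. SAP section 12 says that nothing has changed from the analyses planned in the protocol.

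DLTs are a planned output in both documents. Protocol 13.7 asks for number and percent by cohort and a listing. SAP 10.3 has a DLT line in the overall adverse event summary and a DLT table by system organ class and preferred term. On timing, SAP 2.2 says: "All the analyses presented in this SAP, will be performed after the database lock".

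**The concern.** The population has moderate-to-severe uncontrolled asthma, so severe asthma events are to be expected, and the omitted phrase exists to keep them out of the DLT count. The SAP carries over the other qualifier, the lymphopenia rule, but not this one, and does not declare the difference.

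Safety is the primary endpoint and the dose groups are small. A final table built on the broader wording could show a DLT at a dose where the protocol definition gives none. It could also list as a DLT an event in a subject who was rightly kept on study drug, or two in a cohort for which no DRC meeting was called. Correct conduct would then look like a deviation.

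**Working it through.** No figure in the plan needs reproducing. The check compares the two texts, then sizes one event.

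**1. Conditions side by side**
- Related to study drug: protocol synopsis yes; SAP 10.3 yes.
- CTCAE Grade 3 or higher: yes; yes.
- Lymphopenia rule: yes; yes.
- Not related to underlying asthma: yes; absent.

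The definitions therefore differ for one class only: Grade 3 or higher events judged related both to study drug and to asthma.

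**2. Can that class occur?**
- Protocol section 11 counts worsening of an existing condition as an adverse event.
- Protocol 10.5 includes hospitalization for asthma among its exacerbation criteria, and the Grade 3 description in SAP 10.3 includes an indication for hospitalization.
- Protocol 11.2 sets a low bar for relatedness: "There is at least some possibility that the AE could be related to study drug administration".
- Protocol 11.2 also tells the investigator that "it should be considered as to whether or not the AE is expected to occur due to the underlying disease". This narrows the class, but it is something to weigh, not an exclusion.
- SAP 10.3 treats missing relatedness as related in the summaries. If that rule is applied to the DLT tables, a severe asthma event with a blank causality field would also qualify.

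So the class is small but not empty.

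**3. Are the tables derived from the SAP wording?** The visible text does not say. Protocol 11.5.1 introduces its list with "The investigator will assign the following AE attributes". The list includes severity and "Causality relationship to study drug or study-related procedures", but neither a DLT designation nor relation to asthma. This does not settle the matter. The lymphopenia rule needs a third judgement, on associated infection, which is not in the list either, so even the SAP definition cannot be fully programmed from those attributes. The eCRF itself is not visible.

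**4. Size of one event, if the SAP wording is applied**

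Inputs: cohorts of 8 randomized 3:1; 12 on active drug at the MTD if that cohort is repeated (protocol 7.1). This assumes cohorts filled at 8, without the optional extra subjects.
- Active per cohort: 8 × 3/4 = 6. One event: 0/6 to 1/6 = 16.7%.
- Repeated MTD dose: 0/12 to 1/12 = 8.3%.
- Pooled EQ001, no repeat: 4 × 6 = 24. One event: 0/24 to 1/24 = 4.2%.
- Pooled EQ001, with repeat: 6 + 6 + 6 + 12 = 30, matching the synopsis maximum. One event: 0/30 to 1/30 = 3.3%.

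These are the effects of any single misclassified subject in groups of this size. The documents give no rate for such events, so no probability is attached.

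**5. Size if DLTs identified during the trial are counted:** zero.

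**The case against.** The strongest case against is that DLTs must be classified while the trial runs. Under the synopsis any DLT permanently ends the subject's dosing, and two in one cohort within the assessment period convene the DRC. Someone has to make that call under the protocol long before a SAP table is produced, and the natural source for the final table is that record. This stands. It makes the zero-effect route the likelier one, though no visible text confirms it.

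Three further objections stand in part. The class is small, because investigators weigh the underlying disease when assigning causality and many asthma events would be unrelated under either text. A miscounted event would be visible, because the DLT table shows preferred terms and all adverse events are listed by subject. And the study does no formal hypothesis testing. These limit the harm but do not reconcile the two definitions.

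The reference text also has a limit. Protocol 7.1 points to Section 7.2.1 for the definition, but the visible part of 7.2.1 contains none. Synopsis and body do not always agree: the BMI exclusion is 36 or above in the synopsis and above 36 in section 8.4. What can be shown is a mismatch between the SAP and the synopsis. A reader might infer that the SAP departs from the definition applied in the trial; the visible documents do not establish that.

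A reader might also infer that the broader wording could trigger DRC meetings, halt escalation or lower the MTD. The documents do not support this. Those rules sit in the protocol, and the analyses in the SAP are run after database lock, with DRC reviews based on separate data snapshots.

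**Conclusion.** The mismatch is real but minor. SAP 10.3 omits a condition found in the only visible protocol definition of a DLT, and SAP section 12 does not declare it. If the final DLT summaries follow the SAP wording, each affected subject adds 16.7 percentage points in an active group of 6, 8.3 points at a repeated MTD dose, and 4.2 or 3.3 points in the pooled EQ001 column. If they count the DLTs identified during the trial, which is more likely, nothing changes.

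Confidence is high on the difference in wording. It is lower on any numerical consequence, which depends on a programming choice that the documents do not state. The conclusion takes the synopsis as the reference definition and covers final reporting only.

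**What to change.** In SAP 10.3, add "and not related to underlying asthma" to the DLT definition. The DLT line and table then use the protocol definition and should agree with the DLTs identified during the trial. The cost is one phrase; no new table, analysis set or data collection follows from it.

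Only if DLT classification was not recorded during the trial is more needed: a query on relation to asthma for each Grade 3 or higher drug-related event, settled before lock. Protocol 9.7 says "The Sponsor will be unblinded to treatment assignment", so that judgement should come from the blinded investigator or a blinded CRO physician. The cost is one query per such event.

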Study Day 1 (Baseline) assessments will include the following: a targeted physical examination, vital signs, laboratory tests, anti-EQ001 antibody test, AE and ACQ-6 monitoring, recording concomitant medications, [REDACTED] pulmonary function testing, and measurement of fractional exhaled nitric oxide (FeNO). If appropriate, repeat assessments can be performed within the Screening Period with approval from the Medical Monitor, as needed.

EQ001 or placebo doses will be administered in the clinic; [REDACTED]

All subjects will undergo the following procedures at every visit except Day 4 (Screening; Study Day 1 [Baseline]; and Study Days 8, 15, 29, 43, 57, and 85): Complete (Screening) or interval (all other study days) medical and surgical histories; complete (Screening) or targeted (all other study days) physical examination; vital signs; hematology and serum chemistry laboratory tests; pulmonary function test; FeNO; AE monitoring (including assessments for injection site-related and hypersensitivity reactions); ACQ-6; and recording of concomitant medications and treatments. EQ001 serum levels will be measured at every visit except Screening.

[REDACTED] . [REDACTED]

[REDACTED]

Pregnancy testing for women of childbearing potential (WOCBP) will be assessed at Screening, Study Day 1 (Baseline), and on Study Days 57 and 85. Electrocardiograms will be performed at Screening, Baseline, and on Study Days 8, 57, and 85.

Early Termination or Unscheduled Visit:

Subjects who receive ≥ 1 dose of study drug should be encouraged to complete all study visits. If subjects do not complete all study visits, or terminate early from the study, they will be asked to return to the study site for an Early Termination (ET) Visit within 28 days of the last dose of study drug administration. [REDACTED]

[REDACTED]

[REDACTED]

[REDACTED] In addition, if at any time up to Study Day 85 (or ET) a subject has an unscheduled study visit, all procedures that were conducted at that visit will be collected in the electronic case report form (eCRF) as an unscheduled visit.

[REDACTED]

[REDACTED]

[REDACTED]

[REDACTED]

[REDACTED]
[REDACTED]
[REDACTED]
[REDACTED]
Study drug should be administered so that there are at least 12 days between doses.

Data Review Committee, Dose-Limiting Toxicity, and Stopping Criteria:

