9.4.2 Prohibited Therapies

Treatment with mAb therapeutics other than EO001 is prohibited.

If a determination is made to treat a subject with any prohibited therapies or medications during the study, the Medical Monitor should be informed. Subjects will be asked to remain in the study and complete all study visits through Study Day 85, but no additional study drug will be administered.

Caffeine and other xanthines (coffee, tea, etc.) should be avoided beginning the night prior to each study visit.

Donation of blood products or sperm is not permitted while on study treatment and for 3 months after the last dose of study drug.

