11 ADVERSE EVENTS

An *adverse event* (AE) is defined as any unfavorable and unintended sign (including an abnormal laboratory finding), symptom, or disease or any worsening of a pre-existing condition temporally associated with the use of a study drug, whether or not related to study drug. The AEs that occur after the first dose of EQ001 or during the study treatment and safety follow-up periods will be documented on the AE eCRF. The investigator will assess AE severity and the causality relationship of the AE to study drug. The investigator will treat the subject as medically required to ensure the subject's safety.

Laboratory values that are outside the laboratory reference range should be reported as AEs only if the investigator considered those AEs to be clinically significant.

From the time of signing the ICF through the first study drug administration, all SAEs and nonserious AEs related to protocol-mandated procedures will be recorded on the SAE/AE eCRF. All other untoward medical occurrences observed during Screening, including exacerbation or changes in the medical and surgical history, will be captured on the medical and surgical history eCRF. Details on recording and reporting AEs are provided below. All AEs will be captured through Study Day 85 or the ET Visit.

Investigators should use their clinical judgment to determine whether a subject is to be withdrawn due to an AE. In the event the subject requests to withdraw from study-related treatment or the study due to an AE, the subject should be asked to return for all remaining study visits through Study Day 85. In the event a subject is withdrawn from study, an ET Visit should be completed.

All subjects experiencing AEs, including clinically significant abnormal laboratory values, whether or not associated with use of the study drug, must be monitored until the condition (1) returns to normal, (2) returns to the subject's baseline, (3) the investigator determines the AE has reached a stable outcome and is no longer clinically significant, or (4) the subject is considered lost to follow-up.

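### SAP 10.3 by default tabulates AEs only to 30 days after last dose, so a subject who stops drug but stays to Day 85 has up to 54 nominal days of collected AEs in listings only

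*SAP*

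**What the plan says.** SAP 10.3 (Adverse Events) sets the window for the AE tables: "In general, adverse events occurring within 30 days after last dose of study drug will be included in the AE summaries". The same sentence sends all AEs to the listings. The rule is worded as a general one, and the visible text names no exception. The tables it governs include serious TEAEs, TEAEs of Grade 3 or higher and TEAEs leading to death.

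Protocol Section 11 sets the collection period: "All AEs will be captured through Study Day 85 or the ET Visit".

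The protocol treats subjects who come off drug in different ways:

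- **Withdrawal requested because of an AE (Section 11):** "the subject should be asked to return for all remaining study visits through Study Day 85".
- **Prohibited therapy given (Section 9.4.2):** the subject is "asked to remain in the study and complete all study visits through Study Day 85, but no additional study drug will be administered".
- **Anyone who has had at least one dose (Synopsis):** such subjects "should be encouraged to complete all study visits". Those who leave are asked to attend an ET visit "within 28 days of the last dose of study drug administration".

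The Synopsis stopping criteria begin "Dosing of EQ001 will be permanently discontinued in a subject if any of the following occurs". The list includes any DLT and repeats the point as "Subject experiences a DLT anytime during the treatment period".

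**The concern.** For a subject who stops drug and stays, the AE tables cover a shorter period than the one over which AEs were collected. The shortening can be linked to tolerability, because a DLT ends dosing. If stopping differs between dose groups, or between EQ001 and placebo, the AE columns would cover different periods with nothing in the tables to show it.

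TEAEs and serious TEAEs are components of the primary endpoint (SAP 4.1), and SAP 6.1 plans no hypothesis test. The descriptive tables therefore carry much of the safety result. A serious AE, or a fatal AE, that starts after the cut-off would by default appear only in a listing.

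The window is also narrower than the SAP's practice elsewhere. The visible TEAE definition in SAP 10.3 has no end date. Worst post-baseline laboratory grade (10.4), out-of-range vital signs (10.6) and largest QTcF increase (10.7) carry no 30-day limit in the visible text. Exacerbation time and rate run to last contact (8.1.8, 8.1.10). For example, take an asthma hospitalization on Day 60 after a single dose on Day 1, recorded as both an exacerbation and an SAE. It would count in the exacerbation rate but by default not in the serious TEAE table.

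**Working it through.** **Inputs.** Doses fall on Days 1, 15, 29, 43 and 57, and the final visit is Day 85 (Protocol 7.1). First dose is Day 1 and there is no Day 0 (SAP 6.2). The later dosing visits and the Day 85 visit each have a window of ±2 days (section titles in the protocol's table of contents). The table window is last dose + 30 days (SAP 10.3).

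**The plan's own figure.** Final visit = 57 + 28 = Day 85, as stated.

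**Days omitted for a subject who stops and stays.** Cut-off = d + 30, where d is the last-dose day. Nominal days omitted = max(0, 85 − (d + 30)). With visit windows, the minimum is max(0, 83 − (d + 2 + 30)) and the maximum is max(0, 87 − (d − 2 + 30)), with Day 1 fixed.

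| Last dose | Cut-off | Nominal days omitted | Range with windows | Scheduled visits after cut-off |
|---|---|---|---|---|
| Day 1 | Day 31 | 85 − 31 = 54 | 52 to 56 | 3 (Days 43, 57, 85) |
| Day 15 | Day 45 | 85 − 45 = 40 | 36 to 44 | 2 (Days 57, 85) |
| Day 29 | Day 59 | 85 − 59 = 26 | 22 to 30 | 1 (Day 85) |
| Day 43 | Day 73 | 85 − 73 = 12 | 8 to 16 | 1 (Day 85) |
| Day 57 | Day 87 | 0 | 0 to 2 | 0 |

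If the dosing day is counted as the first of the 30 days, the nominal values become 55, 41, 27, 13 and 0.

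**Who is not affected.** A completer's cut-off is Day 87, past Day 85; the 2-day exception needs a last dose on Day 55 and a final visit on Day 87. A subject who leaves with an ET visit on time is seen within 28 days, which is less than 30, so nothing is omitted.

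**DLT stops.** A DLT on Days 1-29 leaves the last dose on Day 1, 15 or 29. If the subject stays, 54, 40 or 26 nominal days are omitted. The earliest cut-off is Day 31, so the DLT assessment period is always tabulated in full.

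**Illustration for one subject.** If one subject's only event in a row starts after the cut-off, the row is understated by 1/n:

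- dose group, n = 8 × 3/4 = 6: 16.7 points
- repeated MTD group, n = 12: 8.3 points
- pooled EQ001, n = 24 or 30: 4.2 or 3.3 points
- pooled placebo, n = 8 or 10: 12.5 or 10.0 points

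**The case against.** A 30-day window is a defensible choice. It covers the whole 4-week follow-up after the last dose, and dosing is every 2 weeks with a half-life said to support that interval (Protocol 4.6). An event up to 84 days after a single dose, perhaps under another monoclonal antibody, is weak evidence of a drug effect. With at most 40 subjects, a listing of every AE can be read in full. This supports keeping the 30-day tables. It does not support making them the only ones when the longer follow-up was deliberately sought and collected.

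A reader might infer more than the documents support:

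- **That every death after the cut-off drops out of the death table.** The filter is on when the AE occurs, and no filter on date of death is visible. An AE that starts inside the window and later proves fatal is not clearly excluded.
- **That everyone off drug is asked to stay to Day 85.** The explicit requests cover withdrawal requested because of an AE, and prohibited therapy. For a DLT-mandated stop, only the general encouragement in the Synopsis applies. The text of Protocol 7.2.2 is not visible.
- **That the SAP departs from the protocol.** The visible Protocol 13.7 sets no window for AE tables, and Section 13 leaves detailed methods to the SAP.
- **That 54 days is typical, or a strict maximum.** It is the nominal figure for a subject dosed once.

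Two further objections stand. SAP 6.3 and redacted text in SAP 10.3 could qualify the rule. And a full-follow-up table does not equalize follow-up, because subjects who leave are still observed for less time.

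**Conclusion.** The point holds in this limited form, as a cheap improvement. By default, AEs that start more than 30 days after last dose are kept out of the summaries. For subjects who stop and stay, this omits 54, 40, 26 or 12 nominal days of collected follow-up unless the last dose was the fifth.

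The conclusion rests on two assumptions: that the general rule is programmed without exceptions, and that at least one subject stops early, stays, and has a relevant event after the cut-off. The documents do not give the number of such subjects. If it is zero, nothing changes, so the percentage points above show only what one event would do.

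The effect on any one subject's record is also limited. Someone who stopped because of an AE already counts under any TEAE and under TEAEs leading to end of treatment. Only the specific SOC/PT, severity, serious or fatal rows could change. Listings, SAE reporting and DRC review are unaffected.

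**What to change.** In SAP 10.3, keep the 30-day summaries and add TEAE, serious TEAE and fatal-AE summaries for AEs that start between first dose and the later of two dates: the last study visit (Day 85 with its window, or ET) and 30 days after last dose. Under that rule no day collected up to the last study visit is omitted, whatever the last-dose day. In addition:

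- flag AEs that start after prohibited therapy;
- footnote, per group, the number of subjects with an AE after the 30-day cut-off;
- show follow-up time per group with the AE tables, because unequal follow-up remains when subjects leave. SAP 7.1 already derives follow-up duration.

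The cost is SAP wording, one further date filter and one added set of tables, all on data already collected. The downside is that some late or confounded events enter the added tables; the retained 30-day set and the prohibited-therapy flag let a reader see their effect. If no subject is affected, the two sets agree.
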